2.0 Objective(s)

AIM 1: Quantitatively and qualitatively, determine the feasibility of collecting responses on an ecological momentary assessment (EMA) version of the Neuropsychiatric Inventory Questionnaire (NPI-Q), via the Brain CareNotes Mobile Application (BCN), from caregivers randomly assigned to using smartphone technology at differing frequency intervals, compared with a control group with data collected without the mobile health version and only at baseline and 6 months). **H1:** Caregivers in the intervention groups will complete the assessments via smartphone and report an acceptable response burden.

AIM 2: Determine whether more frequent surveillance of BPSD yields more actionable data. **H2:** We expect there to be more occurrences of “actionable data” in the groups (i.e., intervention vs control) or conditions within a group (i.e., weekly vs monthly condition within the intervention group) that have more frequent monitoring. We define actionable data as data that could lead to a change in care plan. This was operationalized by setting “clinically significant” thresholds for NPI-Q symptoms

AIM 3: Explore whether different surveillance intervals are associated with greater improvement in BPSD and CG distress. **H3:** Groups or conditions within a group that receive more frequent surveillance paired with response to “clinically significant” symptoms will have greater improvement in BPSD and in caregiver distress.

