BCN is not intended to function as a medical device. BCN does not meet the software definition of a medical device as clarified in the updated 2019 *FDA Policy for Device Software Functions and Mobile Medical Applications Guidance for Industry and Food and Drug Administration Staff*. Section 201 (h) of the FD&C ACT defines a medical device as "...an instrument, apparatus, implement, machine, contrivance, implant, *in vitro* reagent, or other similar or related article, including any component, part, or accessory", that is "... intended for use in the diagnosis of disease or other conditions, or in the cure, mitigation, treatment, or prevention of disease, in man ..." or "... intended to affect the structure or any function of the body of man or other animals..." and "does not include software functions excluded pursuant to section 520(o) of the FD&C Act." (<https://www.fda.gov/regulatory-information/search-fda-guidance-documents/policy-device-software-functions-and-mobile-medical-applications>).

BCN is intended to be used as a mobile application that helps facilitate communication between caregivers and members of a patient's treatment team. It is not a treatment onto itself.

3.1.3 Feasibility will be measured 5 different ways:

- 1) Completion rate of the NPI-Q through the BCN app by the aMCI or AD caregiver over the 6-month intervention period.
- 2) Quantitative answers to the burden of scale completion question will be asked every time the NPI-Q is completed. *"How burdensome was completion of the prior scale (Answer options: not at all burdensome, mildly burdensome, moderately burdensome, or extremely burdensome)"*.
- 3) Completion rate of the semi-structured BPSD phone questionnaires triggered by "clinically significant" symptoms entered by the caregiver into the BCN application.
- 4) aMCI and AD Caregiver Feasibility and Usability Survey (3mo, 6mo, quantitative).
- 5) aMCI and AD Caregiver Feasibility and Usability Semi-Structured Interview (3mo, 6mo, qualitative).

3.1.4 Usability will be measured 3 different ways:

- 1) System Usability Scale
- 2) aMCI and AD Caregiver Feasibility and Usability Survey (3mo, 6mo, quantitative)
- 3) aMCI and AD Caregiver Feasibility and Usability Semi-Structured Interview (3mo, 6mo, qualitative)

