5.0 Study Design

The purpose of the following randomized control trial is to determine: 1) the feasibility and usability of the Brain CareNotes mobile application (BCN) intervention to deliver ecological momentary assessment (EMA) surveillance of Behavioral and Psychological Symptoms of Dementia (BPSD) and caregiver distress in amnestic mild cognitive impairment (aMCI) or Alzheimer's Disease (AD) caregivers, 2) the optimal surveillance frequency and 3) whether improved BPSD surveillance can improve opportunities to intervene.

The BCN intervention delivers the Neuropsychiatric Inventory Questionnaire (NPI-Q) to caregivers of patients with either aMCI or AD to monitor BPSD and caregiver distress. During the study caregivers in the intervention group will be asked to answer an EMA version of the NPI-Q on the BCN intervention at differing intervals (weekly or monthly).

We propose to enroll 154 aMCI and AD patient-caregiver dyads from our memory care practice at Eskenazi Health, Sandra Eskenazi Center for Brain Care Innovation (SECBCI), an urban safety net hospital in Indianapolis in a 6-month randomized controlled trial of EMA assessment to monitor BPSD compared to enhanced care. Subject dyads will be randomized to either the intervention or control group in a 1:1 ratio (77 per group). The control group will not receive the BCN intervention. However, the caregivers in the control group will be administered most of the same assessments at the baseline, 3-month and final (6-month) visit as the caregivers in the intervention group, except for the two assessments that ask questions related to the mobile application. Caregivers will also participate in semi-structured interview at the baseline visit, final visit and when triggered by "clinically significant" BPSD.

The study design includes six 1-month periods. Those in the intervention group will be nested in a 2 x 6 cross-over design in which they will be randomly assigned to start with 1 of 2 schedules of EMA surveillance frequency (1) weekly or (2) monthly. The intervention participants will then cross-over at the end of each and every month to the other surveillance frequency condition, over a 6-month time horizon. The crossover design allows efficient sample size reduction for the comparison between two higher frequency arms by allowing persons to serve as their own controls for a within person intervention effect. According to standard analysis of cross-over trials, the comparison

[figure not shown]

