of the two EMA surveillance frequency conditions within the intervention group will be tested with a within-subjects test. Co-variates and biological variation including sex will be incorporated into the analysis.

Table 1. Study Characteristics

Stage of Behavioral Intervention Development:	Stage II
NIH Phase III Clinical Trial?	No
Multiple Site Trial?	No
Brief Description of Study Design	
Study participants, 154 caregiver-patient dyads with amnestic mild cognitive impairment (aMCI) or Alzheimer's Disease (AD) Dementia (308 human subjects) will be randomly assigned to Enhanced Care (EC, 77 dyads) or the BCN Intervention + EC (77 dyads).	
Enhanced Care (EC) x (6-mo)	
 • Dementia collaborative care provided through the Sandra Eskenazi Center for Brain Care Innovation (SECBCI). • Services include care coordination, and evidenced based assessment and treat protocols for behavioral and psychological symptoms of dementia (BPSD).
Brain CareNotes (BCN) App + EC x (6-mo)	
 • The Brain CareNotes (BCN) app was developed with a user centered design for patients with MCI and AD, caregivers and healthcare team members. • The BCN app will deliver the Neuropsychiatric Inventory Questionnaire (NPI-Q) to the caregiver to report on the patient's BPSD severity and associated caregiver distress severity. • The NPI-Q delivery frequency will alternate every 30 days between conditions of weekly or monthly delivery. These set frequencies of weekly and monthly, will be re-evaluated and possibly modified based on feedback from the first 10 participants in the intervention arm. • If BPSD as measured by the NPI-Q rises to a set severity threshold then this data will be shared with the patient's treatment team who will contact the caregiver for further evaluation.

Table 2. Defining Clinically Significant BPSD and Responses to BPSD

Clinically Significant BPSD Severity Threshold	
 Clinically Significant BPSD will be defined as when any NPI-Q severity domain = 3 regardless of caregiver distress, or whenever NPI-Q caregiver distress is marked as “moderate” “severe” or “very severe”.

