12.0 Statistical Considerations and Analysis

12.1 AIM 1: Quantitatively and qualitatively, determine the feasibility of collecting responses on an EMA version of the Neuropsychiatric Inventory Questionnaire (NPIQ-EMA) from caregivers using smartphone technology at differing frequency intervals weekly or monthly, or a control group with data collected without the mobile health version and only at baseline and 6 month).

H1: Caregivers in the intervention groups will complete the assessments via smartphone and report an acceptable response burden. We anticipate that the response burden will be comparable to data collected in routine office visits.

Analysis H1: The primary outcomes for AIM 1 are feasibility and usability.

Feasibility will be measured 5 different ways:

- 1) Completion rate of the NPIQ-EMA over 6 months
- 2) Answers to the NPIQ-EMA response burden question every time the NPIQ-EMA is completed: "How burdensome was completion of the prior scale (Answer options: not at all burdensome, mildly burdensome, moderately burdensome, or extremely burdensome)"
- 3) Completion rate of the semi-structured phone interviews triggered by "clinically significant" symptoms
- 4) Post-intervention survey (quantitative)
- 5) Post-intervention semi-structured interview (qualitative) occurring immediately at the end of 6 months.

Usability will be measured in 3 different ways post-intervention:

- 1) System usability scale (SUS) total score
- 2) Post-intervention survey (quantitative)
- 3) Semi-structured phone interview (qualitative).

Quantitative Analysis: For quantitative analyses, there scores are continuous scale scores. Therefore, the intervention group feasibility scores will be compared to the control group's feasibility (response burden question) relative using ANCOVA to adjust for baseline characteristics including baseline demographics. The adjustment for baseline will increase precision and will statistically ensure comparability of the baseline level symptoms, even though random assignment should generally provide approximate comparability across a host of baseline characteristics.

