16.0 Other

16.1 Essential Equipment: We will use the Android Pixel phone by Google as a loaner phone for study subjects (caregivers) who do not have their own smartphone. The phone will be pre-loaded with the EMA version of the NPI-Q delivered by mobile app.

16.2 Potential Problems and Alternative Strategies:

16.2.1 Worsening caregiver burden: One concern of this proposal, is whether EMA monitoring of BPSD creates too much of a burden on the already burdened caregiver. Participants in our 28-day R01 study and in our pilot have not found the EMA pinging of the smartphone to be burdensome. The R01 study population demographics overlap significantly with our anticipated patient-caregiver population. As a safeguard, we will use usability and burden questions from the semi-structured interview from the initial 10 aMCI/AD caregiver-dyads to determine if the burden of answering EMA questions for the caregivers is too great. If that does turn out to be the case we will consider lengthening the surveillance interval or shortening the assessment battery.

16.2.2 Drop off in participation during the monthly response interval: It is possible that participation in the EMA BPSD surveillance might drop off during the two-month block, where BPSD surveillance takes place monthly instead of weekly. To address the potential, drop off in participation during the monthly surveillance block we will observe attrition rates for our first 10 dyads. If attrition rates exceed that of 17% we will make an adjustment to surveillance frequencies dropping the monthly surveillance block and instead continuing with weekly surveillance.

16.3 Summary and Future Directions: The following study looks to improve the care of aMCI/AD patient-caregiver dyads through the study of a BPSD surveillance intervention. Our choice of a weekly/monthly frequency, was a conservative approach in this early work to manage caregiver and provider burden but should evidence indicate high feasibility and value of weekly intervals, a future project could test higher frequencies to identify a frequency of diminishing return. Findings from this study will be used to develop a BPSD surveillance EMA intervention for a future R01 proposal that will improve the access to care and health of AD patient-caregiver dyads. This work will help my maturation into an independently funded investigator.

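### Aim 1 asks about feasibility at weekly or monthly frequency, but the plan defines a single 6-month completion rate and specifies no weekly-versus-monthly analysis of completion

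*Combined protocol and SAP*

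**What the plan says.** **The aim.** Section 2.0 sets out to determine the feasibility of collecting NPI-Q responses "from caregivers randomly assigned to using smartphone technology at differing frequency intervals". Section 12.1 names the intervals: "from caregivers using smartphone technology at differing frequency intervals weekly or monthly".

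**The measure.** Section 3.1.3 gives "Completion rate of the NPI-Q through the BCN app by the aMCI or AD caregiver over the 6-month intervention period". Section 12.1 gives "Completion rate of the NPIQ-EMA over 6 months". Neither states the number of prompts, the denominator or a split by condition.

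**The design.** Section 5.0: "The study design includes six 1-month periods", and "The intervention participants will then cross-over at the end of each and every month to the other surveillance frequency condition". Table 1: "The NPI-Q delivery frequency will alternate every 30 days between conditions of weekly or monthly delivery".

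**The analysis.** The one quantitative analysis in Section 12.1 is an ANCOVA of intervention against control, and the score it names is the response burden question. Section 5.0 says that the control group does not receive the app. Sections 12.2 and 12.3 set out within-group crossover models with period and starting condition, for actionable data (H2) and for symptom and distress scores (H3). Section 5.0 also says, without naming outcomes, that the two frequency conditions will be compared by a within-subjects test.

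**The risk the plan foresees.** Section 16.2.2 raises this as a possibility: "participation in the EMA BPSD surveillance might drop off during the two-month block, where BPSD surveillance takes place monthly instead of weekly". Its check is attrition in the first 10 dyads, with a trigger at 17%.

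**The concern.** The completion rate is the first feasibility measure listed for the primary aim. Every intervention caregiver spends equal time under each frequency but receives several times as many prompts in a weekly month as in a monthly one. A single rate over the 6 months therefore neither shows the two frequencies separately nor, on the most natural definition, weights them equally. The controls cannot serve as a comparator for app completion, and the plan does not apply to this outcome the crossover contrast that could.

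At stake is what the feasibility result can say about frequency. The trial is meant to inform the choice of surveillance interval. Section 16.3 makes a future test of higher frequencies depend on evidence that weekly intervals are feasible, and that calls for a weekly-specific rate.

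**Working it through.** The plan states no prompt count, weighting or completion target, so it has no figure of its own to reproduce here.

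**Inputs**
- Six 1-month periods, alternating every 30 days (Section 5.0 and Table 1). Either starting sequence gives 3 weekly and 3 monthly blocks.
- Intervention arm: 77 dyads randomised (Section 5.0), 64 projected to be analysable (Section 12.4).
- Assumption: *w* = 4 to 5 weekly prompts per 30-day block (30/7 = 4.3), and 1 prompt per monthly block.
- Assumption: completion rate = prompts completed / prompts scheduled.
- The completion percentages below are illustrative.

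**Step 1. Weekly share of scheduled prompts** = 3*w* / (3*w* + 3)
- *w* = 4: 12/15 = 80.0%
- *w* = 30/7: 12.86/15.86 = 81.1%
- *w* = 5: 15/18 = 83.3%

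**Step 2. Pooled rate** = share × weekly completion + (1 − share) × monthly completion

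| Weekly | Monthly | Pooled, *w* = 4 | Pooled, *w* = 5 | Equal-weight mean |
|---|---|---|---|---|
| 90% | 90% | 90% | 90% | 90% |
| 90% | 50% | 82% | 83% | 70% |
| 90% | 0% | 72% | 75% | 45% |
| 60% | 95% | 67% | 66% | 77.5% |

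Example: 0.80 × 0.90 + 0.20 × 0.50 = 0.82. A 40-point fall in monthly completion moves the pooled rate by 7 to 8 points. The last row shows the reverse case: good monthly completion barely lifts a poor weekly rate.

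**Step 3. Sensitivity to the block length.** Section 16.2.2 speaks of a two-month block, against the 1-month periods of Section 5.0. With two-month blocks and *w* = 4, a weekly-first caregiver has 4 weekly and 2 monthly months, a share of 16/18 = 89%. A monthly-first caregiver has 8/12 = 67%. The two sequences pooled equally give 24/30 = 80%.

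**Step 4. Does the Section 16.2.2 check fill the gap?** It counts dyads lost, not prompts answered, and stops at 10 dyads. With 10 dyads, exceeding 17% means 2 or more losses. If true attrition is exactly 17%, the chance of that is 1 − 0.83^10 − 10 × 0.17 × 0.83^9 = 1 − 0.155 − 0.318 = 0.53.

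**Step 5. What a split would offer.** Before attrition, 77 dyads give 77 × 12 = 924 to 77 × 15 = 1155 weekly prompts and 77 × 3 = 231 monthly prompts. As a rough guide, a paired comparison in 64 dyads has 80% power (two-sided 5%) at a standardised within-person difference of about (1.96 + 0.84)/√64 = 0.35, or 0.36 with the t distribution.

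**The case against.** The strongest reply is that H1 is not comparative. It predicts that caregivers will complete the assessments and find the burden acceptable, and an overall rate addresses that. Section 5.0 lists feasibility and optimal frequency as separate purposes, and the frequency contrasts sit in H2 and H3. Section 5.0 also states a general within-subjects comparison of conditions. Burden is recorded at each completion, surveys and interviews add evidence, and Table 1 has the frequencies re-evaluated after the first 10 intervention participants.

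Part of this stands: an overall rate is a legitimate description, and the general sentence shows that a within-person comparison is in keeping with the design. But that sentence does not name completion, Section 12.1 does not carry it through, and the aim as worded specifies weekly or monthly collection.

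Four stronger readings are tempting, and the documents do not support them.
- *Weekly prompts carry 80% of the rate as a matter of fact.* The denominator is not stated. A rate averaged over months would weight the conditions equally, though it still would not show them separately.
- *Monthly drop-off is the plan's main concern.* Section 16.2 raises it as a possibility, second to caregiver burden, and ranks neither.
- *A poor monthly rate would pass as acceptable.* No completion target is given. A caregiver who stops for good during a monthly block also misses later weekly prompts, which lowers the pooled rate. What is masked is skipping monthly prompts while still answering weekly ones.
- *The trial could never answer the question.* The app data would allow a split at any time. The gap is that none is planned, so the denominator, the handling of non-response and the model would be chosen after seeing the data.

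**Conclusion.** The point holds as a gap between the aim and its analysis. Followed as written, the plan yields no completion result by frequency for Aim 1. On the assumptions of completed over scheduled prompts and 4 to 5 prompts per weekly block, weekly prompts make up about 80% to 83% of the single rate, so a monthly shortfall would largely disappear in it. The Section 16.2.2 check only partly mitigates this. The missing contrast does not depend on these assumptions; the size of the masking does. It is worth correcting because the correction is nearly free, but it does not invalidate the trial or the overall rate as a description.

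**What to change.** In Sections 3.1.3 and 12.1:
- Define completion as prompts completed / prompts scheduled, per caregiver per period, and state the scheduled number in a weekly and in a monthly month.
- Report it separately for weekly and monthly months, keeping the pooled 6-month rate as a description.
- Compare conditions within person with a binomial mixed model: condition, period (1 to 6), starting sequence and a caregiver random effect. The H2 model should not be carried over unchanged, because its outcome is one yes/no per month, whereas completion has about 4 prompts in a weekly month and 1 in a monthly month.
- State how prompts due after withdrawal or lasting non-response are counted. Add a sensitivity analysis limited to periods before dropout, so that a loss starting in one condition is not charged to the other.

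Reconcile the block length in Section 16.2.2 with the periods in Section 5.0 and Table 1.

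The cost is a few lines of text and one model on data that the app already records, with no new visits or participants. The monthly estimate rests on 3 prompts per caregiver, against 12 to 15 weekly, so its interval will be wider.

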 - 12) Provision of a \$10 Kroger gift card to both the patient and caregiver following completion of the baseline visit activities.
 - 13) Provision of an Eskenazi Health parking voucher (only if the visit takes place in-person).
- The caregiver in the intervention group will be asked to complete a survey on Behavioral and Psychological Symptoms of Dementia (BPSD) for the person with aMCI or AD for 6 months through either the caregiver's smartphone or a loaner smartphone from the study. The survey is a mobile health version of the

Neuropsychiatric Inventory – Questionnaire (NPI-Q) delivered by the Brain CareNotes (BCN) app. The following additional survey question will be asked following delivery of the NPI-Q, *“How burdensome was completion of the prior scale? (Answer options: not at all burdensome, mildly burdensome, moderately burdensome, or extremely burdensome)”*

- Clinically Significant BPSD will be defined as when any NPI-Q severity domain = 3 regardless of caregiver distress, or whenever NPI-Q caregiver distress is marked as “moderate” “severe” or “very severe”.
-
- When Clinically significant BPSD is present at either the baseline visit, 3-month visit, final (6-month) visit or through completion of a BCN app record then the following actions will be triggered:
 - 1) Automatic free response follow-up questions (via BCN).
 - 2) Automatic notification of study team.
 - 3) Automatic notification of SECBCI clinical team.
 - 4) The research team to contact the caregiver and complete a semi-structured interview and the Caregiver & Environment Assessment for Neuropsychiatric Symptoms.
 - 5) The study team member documents findings and notifies PI and SECBCI clinical team.
- If the participants choose to complete their assessment in person then the study team will call 24-48 hours before the 3-month visit to make sure that in the past 2 weeks the patient and caregiver have not been in contact with anyone diagnosed with COVID-19, and have not developed any symptoms to suggest that they currently have COVID-19. If they choose to complete their assessment over the telephone, then the study team will not make this call.

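### The documents conflict on whether controls answer the response-burden item that the Aim 1 ANCOVA compares between groups, and they state no scoring rule or weekly-versus-monthly analysis for it

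*Combined protocol and SAP*

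**What the plan says.** Section 12.1 makes feasibility and usability the primary outcomes of Aim 1. The second of five feasibility measures is "Answers to the NPIQ-EMA response burden question every time the NPIQ-EMA is completed", with four ordered options running from no burden to extreme burden. Under Quantitative Analysis the plan states: "For quantitative analyses, there scores are continuous scale scores". It then compares the intervention group with the control group's "feasibility (response burden question) relative using ANCOVA to adjust for baseline characteristics including baseline demographics". This is the only inferential analysis that Section 12.1 describes. Under H1 the section adds: "We anticipate that the response burden will be comparable to data collected in routine office visits".

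On prompting frequency, Section 5.0 says in general terms that the comparison "of the two EMA surveillance frequency conditions within the intervention group will be tested with a within-subjects test". Sections 12.2 and 12.3 give the crossover model (period, starting condition, baseline covariates) for actionable data, the two NPI-Q totals, the PSS-14 and the ZBI. Section 12.4 mentions power for paired weekly-versus-monthly tests without naming an outcome.

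**The concern.** A between-group test needs the item to be asked in both groups. Parts of the document place it only inside the app. If it is asked only there, the one stated Aim 1 test has no control data, and an answer about how burdensome a questionnaire was just now cannot be collected afterwards.

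Two further gaps concern the same item. An ANCOVA needs one number per caregiver, but each intervention caregiver is prompted many times and no rule reduces those answers to a score. Aim 1 is also about feasibility at weekly and monthly prompting, and Section 16.2.1 treats burden as a reason to lengthen the interval. Yet no analysis comparing burden between the two frequencies is named.

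**Working it through.** **1. Who is asked, and when.**

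Text pointing to app-only collection:
- Section 12.1 ties the item to completion of the app version of the NPI-Q.
- Section 7.0 introduces it within the description of the intervention caregiver's app survey: "The following additional survey question will be asked following delivery of the NPI-Q".
- Section 5.0: "The control group will not receive the BCN intervention".
- The numbered lists for the baseline, 3-month and final visits in Section 7.0 do not include it.

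Text pointing to both arms:
- Section 3.1.3 has the item asked at each completion of the NPI-Q, which controls also complete at visits.
- Section 5.0 gives controls most of the same assessments, "except for the two assessments that ask questions related to the mobile application". Table 4 marks exactly two rows as intervention-only: the System Usability Scale and the post-intervention survey.
- Table 4 marks the burden row at all three visits without that restriction.

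Text fitting neither:
- Table 4 labels the row as an app item and gives it the asterisk for activities triggered by clinically significant BPSD. Read literally, this contradicts asking every time. If followed, it would select answers by symptom severity.

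**2. The plan's own sample-size figure (Section 12.4).** Inputs: 64 analyzable per arm, two-sided 5%, difference 0.50 SD.
- Noncentrality = 0.50 × √(64/2) = 2.83 on 126 df, giving power 80.1%. This agrees with the stated 80%.
- 128/0.83 = 154.2, against 154 stated.

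These figures presume 64 controls with a score. With 64 intervention caregivers and an assumed 48, 32 or 16 controls answering, power at 0.50 SD is 73.8%, 62.8% or 42.4%. With none, the model cannot be fitted.

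**3. Effect of the scoring rule.** Inputs: three weekly and three monthly months (Section 5.0). Assumption: 4 or 5 prompts in a weekly month and 1 in a monthly month. The counts are scheduled prompts, not completed answers.
- App prompts: 3×4 + 3×1 = 15, or 3×5 + 3×1 = 18.
- Weekly weight in a plain mean: 12/15 = 80%, or 15/18 = 83%.
- With the three visit NPI-Qs counted as well: 12/18 = 67%, or 15/21 = 71%.
- Mean of the six monthly means (app answers): 50%.

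On app answers alone, the plain mean differs from the mean of monthly means by 0.30 to 0.33 times the weekly-minus-monthly difference. Example with scores 0 to 3 and assumed means of 1.0 (weekly) and 0.5 (monthly): (12×1.0 + 3×0.5)/15 = 0.90, against (1.0 + 0.5)/2 = 0.75.

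**4. Precision of the between-group comparison.** Unadjusted, item scored as continuous as the plan does.
- One answer per person: 1.979 × √(2/64) = 0.35 SD half-width for the 95% CI.
- Mean of two answers with within-person correlation ρ: 1.979 × √(2[ρ + (1−ρ)/2]/64) = 0.28 to 0.32 SD for assumed ρ of 0.3 to 0.7.
- Power for an assumed true difference of 0.3 SD, one answer each: 39.1%, so about 61% of such trials would be non-significant.

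**5. Would the last app answer in months 3 and 6 balance the frequencies?** A weekly start gives W,M,W,M,W,M and a monthly start gives M,W,M,W,M,W. Each caregiver is therefore scheduled for one of each in months 3 and 6. With an assumed 70% completion per prompt, the chance of at least one answer is 1 − 0.3⁴ = 99% in a weekly month (4 prompts) and 70% in a monthly month. Weekly answers then make up 0.99/(0.99 + 0.70) = 59%. Balance cannot be assumed and has to come from the model.

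**The case against.** The best defence is that one reading makes most of the text consistent: the item follows every NPI-Q in both arms. Section 3.1.3, the two withheld assessments, the untagged Table 4 row and the ANCOVA itself all fit that reading. The visit lists name instruments, so a one-line follow-up could be left out. Section 7.0 does not say that controls are not asked. The asterisk may be loose too: the CEAN carries it and is nevertheless scheduled at every visit. This stands far enough that a reader should not infer that controls are never asked. It does not settle the matter, because staff working from Section 7.0 would have no instruction to ask controls.

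Three further points stand in part.
- H1 as worded in Section 2.0 requires acceptable burden among intervention caregivers, which needs no control comparison. The between-group test is nevertheless what Section 12.1 specifies.
- Burden may be near the floor. All four pilot caregivers, prompted daily, reported no burden (Section 6.2), and Section 16.2.1 says the same of a 28-day study. If weekly and monthly burden hardly differ, the scoring rule hardly matters. Four caregivers and an indirect study cannot establish that.
- Treating a four-level item as continuous is common. The gap is the missing rule for combining repeats more than the scale.

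A reader might infer that the plan makes no frequency comparison at all. Section 5.0 commits to one in general; what is missing is this item. A reader might also infer that the sponsor will take a non-significant ANCOVA as proof of comparability. The documents state only an expectation, with no margin, so that misreading is a possibility and not a plan.

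**Conclusion.** The point holds and should be fixed. The documents conflict on who answers the burden item and when, and one of the available readings makes the stated Aim 1 ANCOVA impossible. The scoring rule is absent, and no weekly-versus-monthly analysis of the item is named.

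The size of the scoring effect is conditional. The 80% to 83% weekly weight applies to scheduled app prompts only, at 4 or 5 per weekly month, and falls to 67% to 71% once visit answers count. The resulting shift scales with a weekly-minus-monthly difference that the documents do not give. The 0.35 SD half-width is unadjusted and could narrow with covariates.

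The planned sample size is not in error. Completion rate, the remaining feasibility measures and usability are untouched.

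**What to change.** 1. Reconcile Sections 3.1.3, 5.0, 7.0, 8.0 (Table 4) and 12.1. Either ask the item after every NPI-Q in both arms, whatever the symptom level, and remove the app label and asterisk for it in Table 4, or delete the between-group ANCOVA.
2. Add a weekly-versus-monthly analysis of the app burden answers within the intervention arm: a mixed model for ordered categories with period and starting sequence, following Section 12.2.
3. If the between-group comparison is kept, compare control visit answers with intervention app answers in months 3 and 6. Weight the weekly and monthly conditions equally, for example through a repeated-measures model with a condition term. Report the estimate with a 95% CI, and do not treat non-significance as evidence of comparability.

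The cost is one extra four-option question at up to three visits in both arms, plus wording changes. Step 2 uses answers already collected. The between-group interval stays wide, at about ±0.35 SD for one answer per person, so it can exclude only fairly large differences. Deleting the ANCOVA adds no data collection but gives up the comparison with office visits.
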